### *3.3.3 Intraoperative Screen Failures*

A subject who has signed the informed consent, in whom the implant procedure is initiated, and does not meet the intraoperative inclusion criteria will not be implanted with the Axonics SNM System. If the subject is not implanted, the subject will be classified as an “Intraoperative Screen Failure” and will be managed according to section 3.3.2.

### *3.3.4 Implant*

A subject who is implanted with the Axonics SNM System as per the study Protocol will be classified as “Implant.” These subjects are followed in accordance with the follow-up schedule and included in all study analysis.

### *3.3.5 Trial Responders/Non-responders*

At the end of 1-month Trial period, all subjects will be classified as Trial Responders or Trial Non-responders (Figure 3).

A subject is considered a Trial Responder if at the end of the 1-month of Trial period, they achieve 50% or greater reduction in the number of urgency leaks compared to baseline on the 72-hour diary.

A subject is considered a Trial Non-responder if they did not meet the above criteria for Trial Responder.

### *3.3.6 Treatment Responders/Non-responders*

A subject is considered a Treatment Responder if at a given follow-up visit they achieve 50% or greater reduction in the number of urgency leaks compared to baseline on the 72-hour diary.

A subject is considered a Treatment Non-responder if they have analyzable data at the follow-up visit, but did not meet the above criteria for Treatment Responder.

### *3.3.7 Withdrawal*

A subject who becomes inactive in the study due to, for example, physician recommendation, subject choice, loss to follow-up, or death, will be classified as “Withdrawal.”

After a subject has been withdrawn from the study or after a subject has withdrawn his/her consent, for any reason, Axonics will not actively collect any additional data after the point of withdrawal. All open adverse events should be closed or documented as chronic. Data collected up to the point of subject withdrawal may be used for analysis and all post-withdrawal adverse events will be recorded in the subject file.

For a subject that wishes to withdraw from the study, the investigator must deactivate the device, request return of all external components, and explant the device. Subject decisions must be fully documented on the final case report form. A statement personally signed and dated by the subject

about the decision to withdraw should be filed in the subject binder. The center will use the electronic database to document this decision process.

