### 3.5 Study Termination

#### 3.5.1 Study Completion

The study may be closed when the following occurs:

- The Enrollment Cap has been met or eighty-one (81) Trial Responders have reached the 1-month follow-up.
- All the subjects have met one of the following criteria:
  - Subject has completed the final study follow-up visit
  - Subject has a mandated or elective deactivation/explant of the device with completion of required follow-up per protocol
  - Subject is withdrawn from the study or is lost to follow-up

When a subject completes the final study visit, they will be allowed to continue to use the Axonics SNM System and be treated by their physician according to the normal standard of care.

Axonics expects that the study will run to completion prior to being closed. In the case of an unexpected issue, the following contingency plans will be enacted.

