### *5.2.4 Analysis methods*

#### *5.2.4.1 Primary Endpoint*

The primary effectiveness endpoint is that the proportion of all implanted subjects that are Treatment Responders is greater than 50% at 6-months post-activation. If the proportion of Treatment Responders is statistically greater than 50%, the study will be considered to be a success.

As mentioned above, a secondary endpoint analysis will also be conducted in subjects who are "Trial Responders" to allow for a direct comparison to the published SNM literature where analysis at follow-up visits are performed only in trial responders i.e. subjects that have  $\geq 50\%$  improvement in

symptoms after a one-month trial with an external stimulator.

The primary endpoint will be tested for significance based on a one-sided binomial test (such as Fisher's exact test) at a 2.1% significance level to account for two additional early looks as detailed in the Statistical Analysis Plan.

The primary safety endpoint of the study is the rate of adverse events (AEs) through 6-months.

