### 8.6.1 Adverse Event Classification

**Adverse Event (AE)** – any untoward medical occurrence, unintended disease or injury, or untoward clinical signs (including abnormal laboratory findings) in subjects, users or other persons, whether or not related to the investigational medical device. This definition includes events related to any procedure in the protocol. The following are NOT considered AEs:

1. Any event expected to occur during the normal course of treatment that is not untoward.
2. Usual aches and pains following the surgical implant procedure. (Pain that is unusually intense or prolonged may be an AE.)
3. Unusual or uncomfortable sensations during the programming of the device or when the Remote Control is used to change stimulation settings. These occurrences are part of the usual standard of care. If the sensation is not resolved by reprogramming then the event may be considered an AE.
4. Change in the effectiveness of the SNM therapy may change over time, possibly requiring changes in programming parameters.
5. Underlying diseases, recorded at baseline, unless there is an increase in severity or frequency during the course of the investigation.
6. Death should not be recorded as an AE, but should only be reflected as an outcome of a specific SAE.

Any AE experienced by the study subject after informed consent, whether before, during or subsequent to the procedure, must be recorded in the eCRF.

**Adverse Device Effect (ADE)** – adverse event related to the use of an investigational medical device.

- a) This definition includes adverse events resulting from insufficient or inadequate instructions for use, deployment, implantation, installation, or operation, or any malfunction of the

investigational medical device.

- b) This definition includes any event resulting from use error or from intentional misuse of the investigational medical device.

**Serious Adverse Device Effect (SADE)** – An effect that has resulted in any of the consequences characteristic of a serious adverse event related directly to the investigational medical device.

**Serious Adverse Event (SAE)** – adverse event that:

1. Led to death
2. Led to serious deterioration in the health that either resulted in
  - a. a life-threatening illness or injury, or
  - b. a permanent impairment of a body structure or a body function, or
  - c. In-patient or prolonged hospitalization, or

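### Capture of adverse events after withdrawal is not assured: Sections 3.3.7 and 8.6.1 conflict, and any loss biases the 6-month AE rate low

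*Combined protocol and SAP*

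**What the plan says.** Section 3.3.7 sets one rule for every withdrawal, whether the subject revoked consent or was withdrawn for another reason such as physician recommendation: "Axonics will not actively collect any additional data after the point of withdrawal". Data gathered up to that point may be analysed, and "all post-withdrawal adverse events will be recorded in the subject file". On events already under way, it says "All open adverse events should be closed or documented as chronic". For a subject who wishes to withdraw, "the investigator must deactivate the device, request return of all external components, and explant the device".

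Section 8.6.1 states the general recording rule: "Any AE experienced by the study subject after informed consent, whether before, during or subsequent to the procedure, must be recorded in the eCRF". Section 8.11 has the investigator monitor AEs for each enrolled subject. Neither section mentions withdrawn subjects.

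Section 3.5.1 lists, as one way a subject may finish the study, "Subject has a mandated or elective deactivation/explant of the device with completion of required follow-up per protocol". Withdrawal and loss to follow-up are a separate item in that list.

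Section 5.2.4.1 defines the endpoint affected: "The primary safety endpoint of the study is the rate of adverse events (AEs) through 6-months". Section 5.2.3.1 bases AE data on all implanted subjects plus intraoperative screen failures.

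**The concern.** The two recording rules point to different places. Section 3.3.7 itself names a final case report form, a subject binder and an electronic database as separate things, so its subject file is not evidently the eCRF. One site could follow 3.3.7 and another 8.6.1, both in good faith, and report different AE counts for the same history.

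The gap matters most where treatment ends. Deactivation and removal are tied to withdrawal in 3.3.7, and to withdrawal for non-compliance in 7.1, where consent to data collection may still be in force. An event arising from such a procedure may fall on either side of the cut-off, because the cut-off is not placed relative to the procedure.

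At stake is the primary safety rate, together with the event counts and subject rates that Section 1.4 promises for device effects, procedure effects and serious events. A subject who has left still counts in the denominator. An event that stays in a site file may not reach the numerator or the DSMB adjudication described in Sections 1.4 and 7.5. The error can run only one way, towards a more favourable rate.

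**Working it through.** The plan states no expected AE rate, no post-implant withdrawal rate and no rate of events after withdrawal, so it has no safety figure to reproduce. Its 20% attrition assumption (Section 5.2.2) covers the period from enrollment to implant and cannot stand in for withdrawal after implant. The effectiveness sample size and power do not depend on AE capture.

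**Step 1: the rules side by side**

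| Question | 3.3.7 | Other sections |
|---|---|---|
| Does active collection continue after withdrawal? | No, for any reason | 8.11: AEs monitored for each enrolled subject |
| Where do later AEs go? | Subject file | 8.6.1: eCRF, for any AE after consent |
| What happens to AEs open at withdrawal? | Closed or documented as chronic | 3.3.2 and 3.5.2: similar rules for screen failures and study closure |
| When is explant, relative to withdrawal? | Required for a subject wishing to withdraw; order not given | 3.4 advises against removal outside listed cases; 3.4.3 lets an inactive device stay in |
| What follow-up comes after explant? | None stated | 3.5.1 refers to required follow-up; 3.4 and Table 1 give no post-explant schedule |

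**Step 2: numerator and denominator**

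Section 5.2.3.1 keeps every implanted subject in the AE denominator. The missing-data rules in 5.2.4.6 cover effectiveness endpoints only. They count a subject explanted or withdrawn because of an AE as a treatment failure, so such withdrawals are foreseen. No rule says how a subject with incomplete safety follow-up counts in the AE rate.

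**Step 3: size per subject**

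With the 116 implanted subjects of Section 5.2.2, one missed subject is 1/116 = 0.86 percentage points. Intraoperative screen failures would enlarge the denominator and make this slightly smaller.

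**Step 4: illustration on assumed rates**

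Let w be the share of subjects withdrawing before month 6, and q the share of those whose first AE falls after withdrawal and before month 6. If none of those AEs reaches the database, the subject-level rate is understated by w × q, or 116 × w × q subjects.

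- w = 2%, q = 10%: 0.02 × 0.10 = 0.2 points; 116 × 0.002 = 0.23 subjects.
- w = 5%, q = 30%: 0.05 × 0.30 = 1.5 points; 116 × 0.015 = 1.74 subjects.
- w = 10%, q = 30%: 0.10 × 0.30 = 3.0 points; 116 × 0.030 = 3.48 subjects.
- w = 15%, q = 50%: 0.15 × 0.50 = 7.5 points; 116 × 0.075 = 8.7 subjects.

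Both w and q are assumptions. The range of 0.2 to 7.5 points shows how the loss scales and is not an estimate for this trial.

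**The case against.** A reader might infer that post-withdrawal AEs, including complications of removal, are lost from the safety rate. The documents do not support that, for these reasons:

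- Section 3.3.7 does not say that the subject file is the only place of record. Section 8.6.1 has no exception for withdrawn subjects, and Section 5.1.1 asks that applicable AEs reach the sponsor by all possible means. Not collecting actively limits what the sponsor solicits; it does not forbid a site to report.
- The duty to explant attaches to a subject who wishes to withdraw. Removal could therefore precede formal withdrawal, with its AEs captured.
- Ending treatment is not the same as withdrawal. Section 3.5.1 lists them separately, and Section 3.4.3 allows deactivation without calling it withdrawal.
- AEs open at withdrawal must be closed or documented as chronic. That covers the event that prompted the withdrawal.
- A subject who leaves because of an AE already counts in a subject-level rate, and a later event does not move it.
- The safety endpoint has no hypothesis or success threshold. Under Section 5.2.4.1, study success rests on effectiveness alone.

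All of these stand, and they limit both the certainty and the size of the problem. They do not remove it. The open-AE sentence does not reach new events. The point about earlier AEs protects the overall subject-level rate, but not event counts, nor a category such as procedure effects in which the subject had no earlier event. The general rule in 8.6.1 does not settle matters while the section written specifically for withdrawal names another destination.

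**Conclusion.** The concern holds as a contradiction that leaves capture of post-withdrawal AEs in the 6-month primary safety rate not assured. Any events missed bias that rate low, because the subjects concerned remain in the denominator. It does not hold as a finding that such events are lost, or that removal complications necessarily fall after the cut-off.

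The size cannot be derived from the documents. The firm statements are 0.86 points per missed subject on 116, and the condition for a subject-level rate to move: withdrawal before month 6 with a first AE between withdrawal and month 6. No effectiveness result, sample size or power figure changes.

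**What to change.** Amend Section 3.3.7 as follows:

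1. Distinguish stopping the device or study visits from revoking consent to data collection.
2. For subjects who have not revoked that consent, require AEs to be entered in the eCRF, as 8.6.1 does, at least to the 6-month safety cut-off. Use existing site contact or records, and count these events in the primary safety rate.
3. State, for data-collection purposes only, how the point of withdrawal relates to any explant, and define the follow-up to which 3.5.1 refers.
4. State how subjects with incomplete safety follow-up are counted in the AE rate.

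Sections 3.3.7, 3.4, 3.4.3, 3.5.1, 8.6.1 and 8.11 must then be reconciled. Nothing here bears on whether or when a device should be removed; on that the sections disagree among themselves, and the sponsor must resolve it.

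The cost is protocol wording and a few extra eCRF entries, for events that sites are already told to record. Because Section 5.2.2 says all subjects are already enrolled and implanted, use of records after withdrawal may also need consent or ethics wording. The reported AE rate may become slightly less favourable.

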### *3.3.8 Subject Lost to Follow-up*

If a subject is lost to follow-up, the investigator should make a good faith effort to contact the subject with at least three (3) documented communication attempts (at least one of which must be in writing). The investigator should inform the subject of the option to withdraw.

If a subject relocates during the clinical trial, efforts will be made to maintain the subject in the study if reasonable travel expenses allow continued participation, provided payment of travel expenses by the sponsor is permitted by applicable law. Alternatively, the subject may be transferred to another clinical trial site, if one is available in the new geography. If the subject cannot be transferred to another clinical site, then the investigator will withdraw the subject from the study as described above.

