## **3.4 Subject Care**

The following sections contain general guidance on dealing with device explant and/or replacement. Axonics does not recommend the removal of the implanted Neurostimulator except in cases of uncontrolled infection, suspected damage to surrounding tissues that may be worsening because of the implant, or intolerable side effects that are not mitigated with inactivating the system.

The decision to explant or replace an implanted device should be made by the subject with appropriate counsel by the physician on procedural risks. A qualified physician who has been trained in the implant/explant of the Axonics SNM System must perform these procedures according to the device manuals.

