### *3.4.1 Implanted Lead Issues*

In the event that the implanted Tined Lead fails, migrates, or is implanted in an undesired position such that adequate therapy cannot be provided, Axonics recommends revising or replacing the lead. Tined Lead revision and replacement does not require a Neurostimulator replacement, however, the physician has the option to replace the Neurostimulator at that time. If the subject does not wish to undergo a replacement in the case of lead failure, their device should be deactivated. If a Tined Lead replacement occurs, the original activation date shall remain as Day 0.

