### *3.4.3 Deactivating the Axonics SNM System*

In some cases, the subject may elect to leave the device implanted, but no longer activated. Leaving the Tined Lead and/or Neurostimulator implanted does not add significant risk to the subject.

Subjects who elect to leave a device implanted that is not activated must return their external devices to the clinical site.

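### Section 3.3.7 requires explant of the device when a subject asks to withdraw, against the protocol's own care guidance in Section 3.4

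*Combined protocol and SAP*

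**What the plan says.** Section 3.3.7 (Withdrawal) addresses voluntary withdrawal directly: "For a subject that wishes to withdraw from the study, the investigator must" do three things, given in one list as "the investigator must deactivate the device, request return of all external components, and explant the device". It then adds: "Subject decisions must be fully documented on the final case report form". It does not say that explant is one of those decisions.

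Section 3.3.8 (Subject Lost to Follow-up) covers a subject who relocates and cannot be transferred to another site: "then the investigator will withdraw the subject from the study as described above".

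Section 3.4 (Subject Care) takes a different line on removal: "Axonics does not recommend the removal of the implanted Neurostimulator except in cases of uncontrolled infection", or suspected tissue damage that the implant may be making worse, or intolerable side effects that switching the system off does not relieve. On who decides, it says: "The decision to explant or replace an implanted device should be made by the subject with appropriate counsel by the physician".

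Two subsections accept a device that stays in place but is off. Section 3.4.1, on lead problems: "If the subject does not wish to undergo a replacement in the case of lead failure, their device should be deactivated". Section 3.4.3, on deactivation: "the subject may elect to leave the device implanted, but no longer activated". Section 3.4.3 requires only that the external devices be returned, and states that leaving the implanted parts in place adds no significant risk.

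**The concern.** Sections 3.3.7 and 3.4 disagree on two questions: when a device should come out, and who decides. A wish to leave the study is none of the three situations in which Section 3.4 supports removal, yet 3.3.7 makes removal mandatory for that reason alone.

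What is at stake is patient safety. Explant is an operation. A site that reads 3.3.7 literally is told to arrange it for a subject with no clinical need. A site that follows 3.4 instead departs from a mandatory item, and Section 8.15 defines any instance of not following the protocol as a deviation.

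The clause still has subjects to act on. Section 5.2.2 says all subjects had been enrolled and implanted by Revision F, and the synopsis gives 24 months of participation after activation.

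**Working it through.** The plan states no figure on this point, so the main check is a comparison of the text. The arithmetic at the end only sizes the exposure.

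**1. Is explant mandatory in 3.3.7?** Yes. One *must* governs three verbs joined by *and*: deactivate, request, explant. The softer verb, request, applies only to the external components.

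**2. Is there a condition or an alternative in 3.3.7?** No. The only trigger is the subject's wish to withdraw. The section does not refer to 3.4 or 3.4.3.

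**3. Does 3.4 cover the same act?** Yes. It introduces itself as general guidance on explant and replacement and makes no exception for withdrawal.

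**4. How do other sections treat the device?**

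| Section | Situation | What happens to the device |
|---|---|---|
| 3.3.7 | Subject wishes to withdraw | Deactivate and explant, mandatory |
| 3.4 | General guidance | Removal not recommended outside three safety situations; subject decides |
| 3.4.1 | Subject declines replacement of a failed lead | Deactivate |
| 3.4.3 | Some cases, no trigger stated | Subject may keep it implanted and off |
| 7.1 | Withdrawn because the subject or investigator refuses to follow the protocol | Deactivate or explant |
| 3.5.1 | Final visit completed | Subject may go on using it |

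Section 3.3.7 is the outlier. A subject withdrawn under 7.1 for refusing the protocol may have the device simply switched off, while a subject who asks to leave is not given that option. Because completers may keep a working device, its investigational status does not explain the rule. The documents give no other reason for it.

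**5. How many subjects could be affected?** The base is 116, the number of implanted subjects in the sample size justification (5.2.2). The withdrawal rate over 24 months is assumed at 2% to 10%. The share who would want explant anyway, or have a 3.4 indication, is assumed at 0% to 50%.

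- Explants called for = 116 × withdrawal rate: 116 × 0.02 = 2.3; 116 × 0.10 = 11.6.
- Avoidable = explants called for × (1 − share wanting or needing explant).
  - At a 0% share: 2.3 to 11.6.
  - At a 50% share: 116 × 0.02 × 0.5 = 1.2; 116 × 0.10 × 0.5 = 5.8.

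The overall range is about 1 to 12 avoidable explants. These are upper bounds, because some subjects would decline surgery.

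**6. Does 3.3.8 widen the reach?** Its back-reference can be read as applying 3.3.7 to a relocating subject who cannot be transferred. The finding does not depend on that reading.

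**The case against.** The strongest reply is that the protocol, read as a whole, already gives an investigator grounds not to operate. Section 3.4.3 allows deactivation alone, states no trigger, does not exclude withdrawal, and its step of returning external devices matches 3.3.7. The lines in 3.3.7 about documenting the subject's decisions could be taken to include a choice about explant. Section 3.4 is advisory in tone, and its removal advice names only the Neurostimulator, so this is a specific procedure set against general guidance rather than two binding rules in collision. Section 8.16 excepts departures needed to protect a subject's well-being, and Type B in Table 6 provides for departures made on medical judgment to prevent harm. An unwanted explant would also need the subject to agree to surgery. On this view the point is a clarification, and counts built on assumed rates should not raise its importance.

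Much of this is right as a limit on the claim. Section 3.4 is guidance. The documents make neither withdrawal conditional on explant nor surgery possible without the subject's agreement. The counts are only as good as their assumptions. Consent pages and device manuals were not available, so actual practice at withdrawal is unknown. Section 3.4.1 concerns a different situation and is supporting context only.

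It does not remove the conflict. The advisory tone of 3.4 makes matters worse, because a reader weighing a *must* against a *should* will follow the *must*. The documentation lines can equally refer only to the decision to withdraw. The deviation clauses excuse a site that ignores a wrong instruction; they do not correct it.

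**Conclusion.** The concern holds. Section 3.3.7 states a wrong rule: it directs removal at a subject's request to withdraw, without clinical indication, where Section 3.4 advises against removal and leaves the choice to the subject. It should be corrected on patient-safety grounds.

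The textual conflict needs no assumption. Its size does: about 1 to 12 avoidable explants among 116 implanted subjects rests entirely on the assumed withdrawal and preference ranges, and should be read as an order of magnitude. No effect on the primary or secondary endpoints is claimed.

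**What to change.** In Section 3.3.7, keep the first two actions (deactivation and the request for external components). Replace the third with an offer of explant, the decision to be made by the subject with physician counsel per Section 3.4. Notify sites of the change. If 3.3.8 is meant to follow the same rule, its back-reference will then point to the corrected wording.

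With this change, the protocol calls for no explant at voluntary withdrawal unless the subject chooses it with physician counsel, and removal stays available to anyone who wants or needs it. The cost is one clause in a protocol amendment and a site notice, with no added data, visits or subjects.
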